12.2.6.2 Secondary variables

Analyses of the secondary variables will be conducted on the FAS (LOCF) only unless otherwise stated. The secondary variables are:

- Proportion of patient responders with HbA1c \leq 7% after 4 months.
- Proportion of patient responders with HbA1c \leq 6.5% after 4 months.
- Mean FPG levels after 4 months
- Mean SMPG after 4 months.
- OGTT after 4 months in a subgroup of the patients.
- Plasma glucose profiles
- Cardiovascular risk factors, such as total cholesterol, LDL, HDL, triglycerides and CRP, after 4 months.

For the continuous secondary efficacy variables (SMPG, FPG), an ANCOVA will be performed as for the primary analysis.

The categorical efficacy variables including HbA1c responders and hypoglycaemia incidence will be compared across treatment groups applying χ^2 -test methodology.

The remaining secondary efficacy variables are deemed exploratory. Statistical comparisons will be performed at the 5% level of significance on the FAS (LOCF) only:

- All of the above secondary variables and the change from baseline for HbA1c will also be summarised and analysed at other scheduled visits eg, Week 4, Month 2, month 3 as applicable.
- The primary and secondary variables for the reference treatment group will also be compared to placebo and AZD1656 doses.

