- **Primary analysis:** an analysis of covariance will be performed on the change from baseline to month 4 with treatment as a factor variable. A factor with five different levels. One level for each dose regimen of AZD1656, one level for each fixed dose 20mg and 40mg, and placebo as reference group. The primary analysis will be on the last observation carried forward and will be based on the full analysis set. As an additional analysis to the primary analysis, the same model will be fitted to data but with treatment as a factor with six levels, one level for each randomized arm.
- **Secondary analyses:** for the continuous secondary efficacy variables (self-monitored plasma glucose, fasting plasma glucose), an analysis of covariance will be performed as for the primary analysis. The categorical efficacy variables including HbA1c responders and hypoglycaemia incidence (see definition in Section 3.1) will be compared across treatment groups utilising a chi-square test. Analyses of the secondary variables will be conducted on the full analysis set (last observation carried forward) only unless otherwise stated.

Safety: All adverse events will be categorised by body system organ class and preferred term using MedDRA dictionary, and be listed for each patient. In the safety analysis set, adverse events will be reported as frequencies in each treatment group.

Haematology and clinical chemistry data will be listed for each patient and summarised for each treatment group at each visit. Shift tables will also be presented.

Summary of value and change from baseline for electrocardiogram, vital signs, weight and waist and hip measurements will be presented. In addition, summary and shift tables for physical examination will be provided. All data will be presented in listings. Summary of adverse events of special interest, hypoglycaemic events and need for additional glucose lowering treatment will also be presented.

Extension

Safety data obtained from the extension period will be analysed in the same way as data from the 4-month treatment period. All safety data will be presented in the clinical study report. Any efficacy data from the extension period explored by AstraZeneca may or may not be included in the clinical study report.

	PAGE
TITLE PAGE	1
PROTOCOL SYNOPSIS	2
TABLE OF CONTENTS	9
LIST OF ABBREVIATIONS AND DEFINITION OF TERMS	14
1. INTRODUCTION	16
1.1 Background	16
1.2 Research hypothesis	17
1.3 Rationale for conducting this study	18

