1.4.2 Clinical information from Phase I and IIa studies

More than 60 healthy, male volunteers and 120 diabetic patients (males and non-fertile females) have been exposed to AZD1656 in the phase I and IIa studies so far. These studies include evaluation of AZD1656 as monotherapy, as add-on to metformin and as add-on to insulin glargine in T2DM patients. Single doses from 2mg up to 180mg AZD1656 have been given to healthy volunteers during euglycaemic clamp conditions. Regarding patients with T2DM, repeated doses of 10mg up to 300mg daily during 1 week and up to 180mg daily during 4 weeks, have been given. The Phase I and IIa studies also include evaluation of AZD1656 on top of metformin in doses up to 100mg daily for 4 weeks and up to 180mg daily on top of insulin for 4 weeks. AZD1656 has been well tolerated and no safety concerns have been raised during Phase I-IIa. No clinically significant laboratory abnormalities have been observed. There have been no deaths. Two serious adverse events (SAEs) have been reported following AZD1656 exposure in Phase I to IIa; one hospitalisation due to atrial fibrillation and one self-limiting, 16-beat ventricular tachycardia after a hypoglycaemic clamp procedure.

There have been 4 hypoglycaemic events, i.e. events with a plasma glucose below 3 mmol/L (54mg/dL). The events were either asymptomatic, scheduled measurements or associated with mild symptoms. No impaired consciousness or need for assistance from another person to

rescue the patient from the hypoglycaemia have been reported. In addition to these episodes, there have been symptoms suggestive of hypoglycaemia reported but with plasma glucose above 3 mmol/L (54mg/dL). All events with low plasma glucose have responded rapidly to oral carbohydrates. In a study of forced hypoglycaemia in T2DM patients on metformin treatment, the individual symptoms of hypoglycaemia were shown to be similar when induced with AZD1656 + insulin or insulin alone and glucose levels could rapidly be restored by glucagon injections in both groups.

The other reported adverse events (AEs) during treatment with AZD1656 or placebo have not revealed any emerging pattern of side effects related to AZD1656 exposure.

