2.2 Secondary objectives

- To characterise the population PK and PD properties of AZD1656 in type 2 diabetes mellitus patients treated with metformin by utilisation of non-linear mixed effects modelling methodology.
- To evaluate other variables of glucose control (fasting plasma glucose, mean daily self-monitored plasma glucose [7-point measurements], oral glucose tolerance test data and number of responders in terms of HbA1C $\leq 7\%$ and $\leq 6.5\%$, respectively) after 4 months in patients receiving AZD1656 as add-on treatment to metformin compared to placebo as add-on treatment to metformin.
- To evaluate other cardiovascular risk factors, such as total cholesterol, low-density lipoprotein cholesterol, high-density lipoprotein cholesterol, triglycerides and c-reactive protein, after 4 months in patients receiving AZD1656 as add-on treatment to metformin compared to placebo as add-on treatment to metformin.
- To investigate the safety and tolerability of AZD1656 compared to placebo, glipizide by assessments of adverse events occurring during the study (including hypoglycaemic events), blood pressure, pulse, physical examination, body weight, safety laboratory variables and electrocardiogram.
- To explore the safety and tolerability of AZD1656 in patients with severely impaired glucose control during a 4 months treatment period.

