12.2.2 Multiple Treatment Comparisons

For conclusion a hierarchical closed testing procedure will be adopted for the efficacy analyses. Treatment group comparisons will be tested in dose span order whereby comparisons with placebo will commence with the highest dose regimen (randomized patient on 20mg daily titrated to maximum of 200mg daily) tested first, next dose regimen 10mg daily titrated to maximum of 140mg daily, fixed dose 40mg daily and finally the fixed dose 20mg daily. Estimates of the treatment effect and corresponding 95% confidence intervals will be presented together with the p-values for the treatment effect. All tests will be performed at the 5% level of significance.

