12.2.6.1 Primary variable

An analysis of covariance (ANCOVA) will be performed on the change in HbA1c from baseline to the final visit at 4 months, with treatment as a fixed factor and the corresponding baseline HbA1c as a covariate.

The FAS will be applied as the primary analysis set on the LOCF approach whereby for missing assessments (visits), the last observation will be carried forward. Baseline values will not be carried forward.

The PP analysis set based on Observed Case will be applied as supportive analyses to the FAS.

The following additional sensitivity analyses will be performed on the primary variable:

- Observed Case analyses will be performed on the FAS whereby missing intermediate assessments (visits) will be excluded.
- If the primary analyses are significant, an additional analysis adjusting for centre/regional effects will be conducted. The primary efficacy variable will be analysed applying the ANCOVA model including additional covariate for centre/region on both the FAS and PP analysis sets.
- Further exploratory and subgroup investigations will be performed on the primary variable considering effects of other factors including gender. Exploratory analysis methodology will be detailed further in the statistical analysis plan.

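### Responders are tested without baseline HbA1c or a named placebo contrast, and hypoglycaemia is filed as an LOCF efficacy variable although the protocol elsewhere treats it as safety

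*Protocol*

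**What the plan says.** **The test.** Section 12.2.6.2 reads "The categorical efficacy variables including HbA1c responders and hypoglycaemia incidence will be compared across treatment groups applying" a chi-square method. The synopsis (Statistical methods) agrees: these variables "will be compared across treatment groups utilising a chi-square test". Neither place names a covariate, a reference arm or an effect estimate.

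**The question.** The responder objective in Section 2.2 is the result "in patients receiving AZD1656 as add-on treatment to metformin compared to placebo as add-on treatment to metformin". Section 12.2.2, on the efficacy analyses, says "Treatment group comparisons will be tested in dose span order whereby comparisons with placebo will commence with the highest dose regimen", and asks for estimates with 95% confidence intervals. Section 12.2.6.2 lists the glipizide comparisons separately: "The primary and secondary variables for the reference treatment group will also be compared to placebo and AZD1656 doses".

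**Baseline.** The primary ANCOVA is fitted "with treatment as a fixed factor and the corresponding baseline HbA1c as a covariate" (Section 12.2.6.1). Section 12.2.6.2 applies the same approach to FPG and SMPG.

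**Analysis set.** Section 12.2.6.2 opens with "Analyses of the secondary variables will be conducted on the FAS (LOCF) only unless otherwise stated". The synopsis lists classified hypoglycaemic events under safety outcomes, on the whole safety set and again without data after rescue. Section 2.2 puts hypoglycaemic events in the safety objective, against placebo and glipizide. Section 12.2.7 repeats the two safety sets.

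**The concern.** **Responders.** Whether a patient reaches 7% or 6.5% depends strongly on where in the 7.5% to 10% entry range that patient starts. Baseline HbA1c is measured and used in the neighbouring analyses, so leaving it out here is inconsistent. It gives up some precision and leaves any chance baseline imbalance in the comparison. The sentence also does not say which contrast the test delivers or how large an effect will be reported, so it does not connect to Section 12.2.2.

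**Hypoglycaemia.** Carrying a last observation forward has no meaning for whether an event occurred. The only formal hypoglycaemia test sits in a section with no rule for data after rescue. Rescue is basal night-time insulin added to randomized treatment (Sections 3.1.6 and 5.6.1), and Section 1.4.2 itself reports hypoglycaemia induced with insulin alone. If rescue is more frequent on placebo, which is plausible but not quantified in the protocol, insulin-related events would accumulate there and blur the AZD1656 comparison.

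**Working it through.** **1. The plan's own figure.** The protocol gives no power for responders or hypoglycaemia. Its only sample size (Section 12.3: difference 0.7, SD 1.4, two-sided 5%, 90% power) reproduces:

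- Normal formula: n = 2(1.960 + 1.282)² × 1.4² / 0.7² = 2 × 10.507 × 4 = 84.1, so 85.
- Noncentral t: 85.03, so 86 (power at 86 is 90.3%).
- With 4% drop-out: 86 / 0.96 = 89.6, so 90.

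**2. Effect of adjusting responders for baseline.** The protocol gives no HbA1c distribution, so these inputs are assumptions:

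- Baseline b: normal, mean 8.4, SD 0.65, truncated to 7.5–10.
- Month-4 value on placebo: b − 0.3(b − 8.4) − 0.3 + error. AZD1656 is 0.7 lower.
- Error SD 1.1 or 0.8; 1,500 trials per setting.
- Pearson chi-square against the likelihood-ratio test in a logistic model with treatment and baseline.

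| Threshold | Error SD | AZD1656 v placebo (n) | Responders, placebo / AZD1656 | Chi-square power | Adjusted power | Change (points) |
|---|---|---|---|---|---|---|
| ≤7% | 1.1 | 90 v 90 | 15.6% / 34.6% | 86.4% | 88.5% | +2.1 |
| ≤7% | 1.1 | 45 v 90 | 15.8% / 34.4% | 69.5% | 70.0% | +0.5 |
| ≤7% | 0.8 | 90 v 90 | 9.3% / 30.1% | 95.4% | 97.0% | +1.6 |
| ≤7% | 0.8 | 45 v 90 | 9.3% / 30.0% | 85.6% | 88.1% | +2.5 |
| ≤6.5% | 1.1 | 90 v 90 | 7.3% / 20.2% | 71.1% | 74.5% | +3.4 |
| ≤6.5% | 1.1 | 45 v 90 | 7.5% / 20.3% | 58.6% | 57.6% | −1.0 |
| ≤6.5% | 0.8 | 90 v 90 | 2.9% / 13.6% | 78.5% | 79.1% | +0.5 |
| ≤6.5% | 0.8 | 45 v 90 | 2.9% / 14.0% | 66.1% | 65.5% | −0.5 |

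A second set for ≤7%, with error SD 0.7 or 1.0, gave 80% to 83% and 89% to 92% (86 v 86), and 64% to 65% and 77% to 81% (43 v 86). The overall range is therefore about −1 to +4 points. Repeating the first model with error SD 1.4 stayed inside it.

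**3. Type I error.** With no treatment difference, the chi-square rejected in 4.1% to 5.3% of trials, so it is valid. The adjusted test rejected in 4.9% to 6.4% at ≤7% and 5.8% to 7.7% at ≤6.5%. The Monte Carlo standard error is √(0.05 × 0.95 / 1500) = 0.56 points, so the adjusted test is somewhat liberal at ≤6.5%, where responders are few. Part of any gain there is not real power.

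**4. Chance imbalance.** With baseline SD at most 0.65, the standard error of the baseline difference is at most 0.65 × √(2/90) = 0.10 for 90 v 90, and 0.65 × √(1/90 + 1/45) = 0.12 for 90 v 45. Under the model, 70% of this carries into month-4 HbA1c: about 0.07 and 0.08, against a planned effect of 0.7.

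**5. Where hypoglycaemia belongs.**

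| Place | Class | Data set |
|---|---|---|
| Synopsis, Statistical methods; Section 12.2.6.2 | categorical efficacy variable, chi-square | FAS with LOCF, no post-rescue rule |
| Synopsis, Outcome variables | safety | safety set, with and without post-rescue data |
| Section 2.2 | safety objective, v placebo and glipizide | not stated |
| Section 12.2.7 | safety variables | both safety sets |

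The first row cannot be reconciled with the others as written. The synopsis also points to Section 3.1 for the definition of incidence, while the three event categories are in Section 11.2, so which of them count is not fixed.

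**The case against.** **A reader might infer a single omnibus test of all arms.** That would be serious. Under assumed rates of 35% responders on glipizide and 15% in every other arm, a six-arm chi-square rejects 91% of the time with AZD1656 inert. But the text does not say all arms or one global test. Section 12.2.2 prescribes comparisons with placebo for the efficacy analyses, the primary model has five levels without glipizide, and glipizide comparisons are listed separately. Pairwise tests are at least as plausible, so the 91% describes a design that the protocol does not clearly state. What stands is that the sentence should name its contrast.

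**A reader might infer that chi-square breaks down for rare hypoglycaemia and that Fisher's test is needed.** Section 1.4.2 says "There have been 4 hypoglycaemic events" in more than 180 exposed people. At 4/180 (one event per person assumed), expected counts are 4/180 × 90 = 2.0 and 4/180 × 45 = 1.0. But that rate comes from AZD1656 exposure of at most 4 weeks and cannot be applied to 4 months, nor to glipizide or placebo. Low counts also do not inflate error here: at assumed event rates of 1% to 10%, exact Pearson size is 1.1% to 5.1% (90 v 90) and 3.1% to 4.7% (90 v 45). Fisher's size is 0.02% to 3.3%, so it is more conservative.

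**Adjustment is a preference, and safety reporting already exists.** Both are largely fair. Omitting baseline does not bias a randomized comparison. Sections 12.2.7 and 12.2.7.1 already summarise hypoglycaemia on the safety sets and tabulate its symptoms. Few patients should fall between the safety set and the FAS, because fasting glucose is measured from week 1. An analysis plan that is not shown may settle the contrasts. None of this removes the protocol's own classification of hypoglycaemia as efficacy under LOCF.

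**Conclusion.** The point holds as a modest one on secondary analyses.

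- **Responders:** the stated test is valid but inconsistent with the rest of the plan. Adjustment is worth about −1 to +4 points of power: roughly +0.5 to +4 at ≤7%, and mixed at ≤6.5%. It also removes a small chance-imbalance component. These figures rest on assumed HbA1c distributions.
- **Hypoglycaemia:** its filing as an efficacy variable on the FAS with LOCF contradicts the synopsis outcome list and Sections 2.2 and 12.2.7. The consequence is that the formal comparison includes events after rescue insulin. Its size cannot be computed, because the protocol gives no rescue rates.

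The documents do not support saying that an omnibus test is specified, that the chi-square fails with sparse counts, or that an exact test is required. The primary HbA1c conclusion is not affected.

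**What to change.** - **Responders:** replace the chi-square sentence with logistic regression on treatment and baseline HbA1c, each AZD1656 arm against placebo in the Section 12.2.2 order, reporting the odds ratio with 95% CI. Also report raw proportions by arm. The odds ratio is conditional on baseline, and the model may fit poorly at ≤6.5% in the 45-patient arms, so name a fallback in advance, such as a penalised-likelihood fit or the unadjusted comparison.
- **Hypoglycaemia:** remove it from the efficacy variables in the synopsis and Section 12.2.6.2. Compare it on both safety sets (all data, and without post-rescue data), without LOCF, each AZD1656 arm against placebo and against glipizide, with a risk difference and confidence interval. State which Section 11.2 categories count, and correct the synopsis cross-reference.

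The cost is protocol or analysis-plan wording and minor programming, with no new data. It should be settled before the sponsor is unblinded at the 4-month database lock.

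### HbA1c responder rates are tested by a valid but unadjusted chi-square that leaves out baseline HbA1c and is not worded to match the ordered regimen-versus-placebo contrasts of Section 12.2.2

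*Protocol*

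**What the plan says.** - **Responder test.** Section 12.2.6.2: "The categorical efficacy variables including HbA1c responders and hypoglycaemia incidence will be compared across treatment groups applying" chi-square methodology. The synopsis (Statistical methods, secondary analyses) says these variables "will be compared across treatment groups utilising a chi-square test". Neither place names a covariate, a contrast or an effect measure.
- **Primary model.** Section 12.2.6.1 analyses the change in HbA1c by ANCOVA, "with treatment as a fixed factor and the corresponding baseline HbA1c as a covariate".
- **Continuous secondary variables.** Section 12.2.6.2: "For the continuous secondary efficacy variables (SMPG, FPG), an ANCOVA will be performed as for the primary analysis".
- **Hierarchy.** Section 12.2.2: "For conclusion a hierarchical closed testing procedure will be adopted for the efficacy analyses". It continues: "Treatment group comparisons will be tested in dose span order whereby comparisons with placebo will commence with the highest dose regimen". It also requires that "Estimates of the treatment effect and corresponding 95% confidence intervals will be presented together with the p-values for the treatment effect".
- **Objective.** Section 2.2 lists the responder counts among the variables to be evaluated "after 4 months in patients receiving AZD1656 as add-on treatment to metformin compared to placebo as add-on treatment to metformin".

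**The concern.** A responder is the primary variable cut at a threshold. The primary analysis and the continuous secondary analyses are ANCOVAs with a baseline covariate. The responder analysis drops it, and no reason is given. The information lost is relevant: a patient who starts at 7.5% needs a fall of 0.5 points to reach 7%, and one who starts at 10% needs a fall of 3.

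The second issue is alignment. Section 12.2.2 and the secondary objective want regimen-versus-placebo comparisons, and Section 12.2.2 adds an estimate and interval. A chi-square described only as running across treatment groups leaves open which groups enter the table, and it yields a p-value without an effect size.

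At stake are some precision on a named secondary objective and a choice of contrast that could still be made after the data are seen.

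**Working it through.** **1. Group sizes.** Section 12.3 plans for a difference of 0.7, SD 1.4, 90% power and two-sided 5%. Normal approximation: n = 2 × (1.960 + 1.282)² × (1.4/0.7)² = 2 × 10.51 × 4 = 84.1, so 85. The t-test solution is 85.03, so 86, with power 0.903 at 86. The stated 86 is reproduced. Taking the same dropout in the 45-patient fixed-dose arms gives 45 × 86/90 = 43 evaluable. The protocol states no responder rate or power for the responder analysis, so everything below rests on assumptions.

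**2. How strongly baseline drives response.** Assume a placebo change of −0.1, no dependence of change on baseline, and the SD range of 1.1 to 1.4 from Section 12.3. Then P(HbA1c ≤7% | baseline b) = Φ((7 − b + 0.1)/SD).

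| Baseline | SD 1.1 | SD 1.4 |
|---|---|---|
| 7.5 | Φ(−0.36) = 36% | Φ(−0.29) = 39% |
| 10 | Φ(−2.64) = 0.4% | Φ(−2.07) = 2% |

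Averaged over an assumed truncated-normal baseline, about 24 to 31% of placebo patients starting below 8% reach 7%, against 2 to 6% of those starting above 9%.

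**3. What adjustment buys at the 7% threshold.** Simulation assumptions: baseline truncated normal on 7.5 to 10 (centre 8.5, SD 0.7), placebo change −0.1, true effect 0.7, slope of change on baseline 0 or −0.3. Implied responder rates are 10 to 17% on placebo and 26 to 31% on active treatment.

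- Pairwise chi-square power, 86 v 86, all four regimens effective: 76% and 70% at SD 1.1 (slope −0.3 and 0); 62% and 58% at SD 1.4.
- Cochran-Mantel-Haenszel stratified by baseline category: gain of about 1 to 4 points at 86 v 86, and 0.5 to 2 points at 43 v 86.
- A likelihood-ratio logistic model shows gains of about 2 to 6 points, but part of that comes from a slightly liberal test.
- Type I error is near 5% for both the chi-square and the stratified test.

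With a narrower baseline distribution (mean 8.6, SD 0.57), power at 86 v 86 rises from 74% to 76% at SD 1.1, and by under 1 point at SD 1.4.

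**4. Chance imbalance.** Under that narrower distribution, a baseline difference of 0.2 points between arms (about 2 standard errors) shifts the unadjusted responder difference by about 3 percentage points, against a true difference of about 15.

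**5. Why the contrast should be named.** Suppose the top regimen had no effect and the other three had 0.7. A single five-group chi-square would reject in 72 to 88% of runs, and the top-versus-placebo test in about 5%. A global result could not serve as the first step of the hierarchy. This illustrates the need for clear wording. It does not show that the plan intends a global test.

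**6. The sparse 6.5% threshold.** In null simulations the chi-square rejected in about 4 to 5% of trials, so it is not anti-conservative. Likelihood-ratio logistic regression at 43 v 86 rejected in about 8.5%.

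**The case against.** The unadjusted test is protected by randomisation and holds its level. This is a Phase II dose-finding study, the continuous form of the same variable is the primary analysis and is already baseline-adjusted, and no primary conclusion depends on the responder test. A 2-standard-error imbalance is the kind of chance event that the 5% level already allows for. All of that stands, and it is why the point is an improvement and not an error.

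A reader might go further and infer that the plan gives no regimen-versus-placebo result for responders. The protocol does not support that. Section 12.2.2 states the contrasts for the efficacy analyses, the objective in Section 2.2 compares AZD1656 with placebo, and the last bullet of Section 12.2.6.2 compares the reference group with placebo and with the AZD1656 doses. Read together, these point to pairwise tests, and the chi-square sentence does not exclude them.

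A reader might also infer that a glipizide effect alone could make the test significant. That needs a single global test that also contains the glipizide arm, and no section specifies one. The synopsis gives the primary model five levels without glipizide, and Section 12.2.6.2 handles the comparator separately.

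Nor do the small expected counts at 6.5% show that the chi-square fails there; its simulated error rate stayed at or below about 5%.

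One reply remains. The choice of test was not left open for the SAP. The protocol fixed it in two places, without the covariate and without an effect measure.

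**Conclusion.** The concern holds in a limited form. The chi-square is valid but less precise than it need be, because it omits a strongly prognostic baseline value that the trial already collects and uses in its primary model. Its wording does not carry over the contrasts, estimates and intervals of Section 12.2.2. The expected gain from stratifying is roughly 0.5 to 4 power points at the 7% threshold, with type I error near 5% either way.

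These figures rest on assumed responder rates, an assumed baseline distribution and a true effect of 0.7. They also treat the enrolment limits of 7.5 to 10% as limits on baseline, although baseline is normally the Visit 3 value. The case for change is that the gain is free, not that it is large. It applies to HbA1c responders; the baseline argument does not carry over in the same way to hypoglycaemia incidence, which shares the sentence.

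**What to change.** In Section 12.2.6.2 and the synopsis, replace the responder part of the sentence along these lines: the proportions with HbA1c at or below 7% and at or below 6.5% at 4 months will be compared between each AZD1656 regimen and placebo, in the order of Section 12.2.2, by a Cochran-Mantel-Haenszel test stratified by baseline HbA1c category; the stratified difference in proportions will be given with its 95% confidence interval; the unadjusted chi-square will be supportive.

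Fix the category boundaries before unblinding; the SAP is a suitable place. Leave the chi-square for hypoglycaemia incidence. Do not substitute likelihood-ratio logistic regression at the 6.5% threshold, given its inflated error in the small arms.

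The cost is one sentence in two places and negligible programming. It needs no new data and no change to sample size or visits.
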